# **Probiotics as Adjuvant Treatment for Bacterial Vaginosis**

**NCT03894813**

**2021-02-20**

## Study Protocol with SAP

This study was a single-centre, prospective, parallel-group, randomized, controlled study. Women who came to the gynaecological clinic of Peking University Shenzhen Hospital, China, between March 2019 and June 2019 with abnormal vaginal discharge symptoms were recruited, and eligible subjects were informed of the study protocol and enrolled in the study. The inclusion criteria were women aged between 18 and 65 years old, premenopausal women, women with a history of sexual activity, and women with a Nugent's Gram stain score of 7 or higher. The exclusion criteria were mixed vaginitis, such as vulvovaginal candidiasis (VVC), Trichomonas vaginalis (TV) infection, *Chlamydia trachomatis* (CT) infection or gonococcal vaginitis; planning for or being pregnant; breast-feeding; pelvic inflammatory disease; allergy to metronidazole; currently using antibiotics; long-term use of contraceptives or immunosuppressants or anaphylactic constitution; and a history of systemic organic diseases or psychiatric diseases. The study was conducted in accordance with the Declaration of Helsinki, was approved by the Medical Ethnic Committee of PKUSZH (with the Unique Protocol ID: PUShenzhenH2018-016) and was first posted on ClinicalTrials.gov (NCT03894813) on March 26, 2019. Informed consent was obtained from all subjects involved in the study.

The sample size was calculated based on the non-inferiority test (<https://www.cnstat.org/samplesize/12/>), which referred to Gregor Reid et al, who carried out studies with the same Lactobacillus strains administered orally to women with bacterial vaginosis (BV). The relevant parameters were determined as follows: test level  $\alpha=0.05$ , test power  $1-\beta=0.80$ ,  $Pt=0.90$ ,  $Pc=0.75$ ,  $Nt:Nc=1:1$ , boundary value  $\Delta= -0.068$  (excellent), and Fisher's exact test. As a result, the sample size of each group was calculated as 50 patients, 100 patients in total. Considering a loss to follow-up rate of 20%, a sample size of 120 patients was finally determined, with 60 patients in each group.

After obtaining written informed consent, the participants were first asked to complete a questionnaire on demographic characteristics, reproductive health and sexual behaviour. They were subsequently randomly assigned to either the metronidazole group or the adjunctive probiotic group according to the random number table. The study was not blinded to the researchers or the patients. Starting from the enrolment day, the participants in the adjunctive probiotic group received orally administered probiotic drinks containing *L. rhamnosus* GR-1 and *L. reuteri* RC-14 ( $\geq 1 \times 10^9$  CFU per day, for 30 days) and vaginally administered metronidazole suppositories (0.2 g per day, for 7 days), and the participants in the metronidazole group received metronidazole vaginal suppositories only. Clinical follow-up visits were scheduled at 30 and 90 days after starting treatment. The intervention products were dispensed by the investigator at the initial visit, and the compliance of participants was assessed by counting returned containers and filling out a questionnaire. The feasibility, acceptability and adherence to the administered products; vaginal symptoms; and

adverse events (AEs) were also assessed by self-report in medication diaries and questionnaires at follow-up visits. Therapy was initiated after the enrolment visit and suspended when menstruation began and continued immediately when it finished. Patients were asked to avoid sexual intercourse and vaginal douching during the first 7 days of treatment with metronidazole suppositories.

General information and clinical signs and symptoms of BV, including homogeneous and thin vaginal discharge, unpleasant odour (such as a “fishy” smell) and vulvar discomfort (such as itching or burning), were recorded at 0 day, 30 days and 90 days. The efficacy outcome was evaluated by the cure rate according to per-protocol (PP) analysis, which was the percentage of participants who did not present with BV (defined by Nugent score  $< 7$ ) at any of the follow-up visits. Those with a Nugent score  $\geq 7$  in the 30-day follow-up was excluded from the trial, but when we evaluate the overall recurrence rate of the 90-day follow-up, these participants were still included in. At each follow-up visit, patients were requested to report any unexpected symptoms during the study period. AEs were recorded in the case report form (Table S1).

The diagnosis criteria of BV were based on Nugent Gram stain scoring of vaginal smears. The Gram-stained smear slides were examined microscopically, and the number of bacterial cells with different morphotypes was counted under  $1000 \times$  magnification. Each slide was identified according to Nugent score. A Nugent score of 0-6 was considered BV negative and of 7-10 was considered BV positive. The Gram stains were analysed in a double-blind manner by two experienced cytology technicians.

This study was a single-centre randomized controlled trial with two arms allocated at a ratio of 1:1. SPSS 13.0 software was applied to generate a random number table, and the random order was assigned depending on the order of enrolment.

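### An add-on probiotic trial is sized only for non-inferiority: the planned 80% is not power to show added benefit, which is about 40% by Fisher's exact test, the one test the plan names

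*Combined protocol and SAP*

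**What the plan says.** All references are to the Combined protocol and SAP, section Study Protocol with SAP.

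- **Comparison.** The title calls the probiotic an adjuvant treatment. One arm receives the probiotic drink plus metronidazole suppositories; in the other, "the participants in the metronidazole group received metronidazole vaginal suppositories only".
- **Sizing.** "The sample size was calculated based on the non-inferiority test". The parameters are α 0.05 (sidedness not stated), power 0.80, Pt 0.90, Pc 0.75, 1:1 allocation and a boundary of -0.068. The list closes with "excellent), and Fisher's exact test". It gives 50 per group. "Considering a loss to follow-up rate of 20%, a sample size of 120 patients was finally determined", that is 60 per group.
- **Analysis.** "The efficacy outcome was evaluated by the cure rate according to per-protocol (PP) analysis". Cure means no BV (Nugent score below 7) at follow-up, with visits at 30 and 90 days. Patients positive at day 30 leave the trial, but "when we evaluate the overall recurrence rate of the 90-day follow-up, these participants were still included in". No test, interval or success criterion is attached to the cure rate or to the recurrence rate.
- **Timing.** Recruitment ran from March to June 2019. The study "was first posted on ClinicalTrials.gov (NCT03894813) on March 26, 2019". The text is in the past tense and dated 2021-02-20.

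**The concern.** Nothing is taken away from the patients who receive the probiotic. Non-inferiority is informative when a new treatment replaces an established one and some loss of effect might be accepted. Here it asks only whether adding a product leaves cure at most 6.8 points worse, which does not show that the product adds anything.

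Two misreadings follow. A met margin can be taken as evidence that the adjuvant works, and the 80% can be taken as the chance of showing that it works. Conversely, if no difference is shown, readers may count that as evidence against benefit when the trial had well under 80% power to find one.

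The named test adds to the difficulty. Fisher's exact test in its ordinary form tests for a difference and has no place for a margin, so it cannot carry out the non-inferiority test on which the size rests.

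**Working it through.** **Inputs.** From the sample-size paragraph: Pt = 0.90, Pc = 0.75, margin -0.068, α = 0.05, power 0.80, 50 per group, 60 enrolled per group, 20% loss. Analysed numbers considered: 60 × 0.80 = 48, the planned 50, and all 60. Assumptions: 0.90 and 0.75 apply to the analysed cure rate (the plan ties them to no visit), and metronidazole is given alike in both arms (dose and duration are stated for one arm only).

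**Step 1: reproduce the 50.** The distance from the margin is 0.90 - 0.75 + 0.068 = 0.218, and

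n = [z(1-α)·s0 + z(0.80)·s1]² / 0.218²

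- s1² = 0.90 × 0.10 + 0.75 × 0.25 = 0.2775, so s1 = 0.5268.
- Farrington-Manning restricted rates under a difference of -0.068 are 0.776 and 0.844. So s0² = 0.776 × 0.224 + 0.844 × 0.156 = 0.3055 and s0 = 0.5528.
- At one-sided 0.025: (1.960 × 0.5528 + 0.8416 × 0.5268) / 0.218 = 1.5267 / 0.218 = 7.003. Squared, this is 49.05, rounded up to 50.

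Other conventions give 47.1 (pooled) and 45.8 (unpooled) at one-sided 0.025, and 36.1 to 38.5 at one-sided 0.05. Reading the boundary as a superiority margin of +0.068 (distance 0.082) would need about 324 per group at one-sided 0.025 (unpooled). The stated 50 therefore fits only the non-inferiority direction.

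**Step 2: superiority power at the same rates.** Sum over every possible pair of cure counts x and y:

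Power = Σx Σy Bin(x; n, 0.90) · Bin(y; n, 0.75) · 1{rule met}

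| Rule | n = 48 | n = 50 | n = 60 |
|---|---|---|---|
| Fisher, two-sided 0.05 | 38.6% | 41.0% | 49.4% |
| Newcombe 95% CI above 0 | 48.2% | 50.4% | 57.9% |
| Chi-square, two-sided 0.05 | 51.2% | 53.0% | 58.5% |
| Newcombe 95% lower limit above -0.068 (non-inferiority) | 80.6% | 83.2% | 89.0% |

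Hand check at n = 50, normal approximation with pooled SD √(2 × 0.825 × 0.175) = 0.5374: (0.15 × √50 - 1.960 × 0.5374) / 0.5268 = 0.014, hence power of about 50.6%.

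One-sided 0.05 does not close the gap: Fisher 52 / 54 / 63%, chi-square 62 / 64 / 71%. For 80% superiority power, the pooled normal formula gives (1.960 × 0.5374 + 0.8416 × 0.5268)² / 0.15² = 99.5, so about 100 per group. Exact Fisher needs about 110 (80.4% at 110). Both are before loss.

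**Step 3: what a met margin shows.** With 75% cured in both arms, the Newcombe lower limit exceeds -0.068 in 12.1 / 12.2 / 13.9% of trials at 48 / 50 / 60 per group. A lower limit above 0 occurs in about 2.5%. At the assumed 0.90 vs 0.75, 32 / 33 / 31% of trials meet the margin with an interval that includes 0. For example, 43/50 vs 38/50 has a lower limit of -0.056 and Fisher p = 0.308.

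**Step 4: the choice of method matters.** At 50 per group and the assumed rates, the Newcombe interval lies above 0 while Fisher p exceeds 0.05 in 9.5% of trials; the reverse never occurs. For example, 54/60 vs 45/60 gives +1.3 to +28.3 points and Fisher p = 0.053.

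**Step 5: the denominator matters.** If 0.90 and 0.75 are day-30 rates and day-30 failures are dropped from a day-90 analysis, 48 per group becomes 48 × 0.90 ≈ 43 and 48 × 0.75 = 36. If the same rates then applied again, power would be 37% (Fisher) or 42% (Newcombe).

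**The case against.** **The plan is open about non-inferiority, and its figure reproduces.** Both stand. A reader might infer that the sample size was miscalculated; Step 1 shows otherwise. The 80% is valid for the hypothesis stated, and the documents themselves make no claim of benefit, so the harm lies in how a result might be read. What remains is that this hypothesis does not answer the question posed by an add-on comparison, and the plan gives no reason for preferring it although it assumes a 15-point advantage.

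**The plan does name a test and a level.** A reader might infer that it has no decision rule at all. That goes too far. Fisher's exact test and α 0.05 stand among the sizing parameters and can fairly be taken as the planned comparison. On that reading the defect is a conflict between a difference test and a margin. The text does not settle it, because neither efficacy analysis has a test or criterion attached.

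**A confidence interval could decide both questions.** A single 95% interval read against 0 and -0.068 is coherent and needs no split of α. But the text postdates recruitment, and the Newcombe interval is the more lenient rule: Step 4 shows that the disagreements run one way only. Making it decisive now would replace the only named test with an easier one. This objection stands and shapes the fix.

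**The power figures are scenario-dependent.** True. They rest on rates tied to no visit, and on a per-protocol set without an adherence threshold: "the compliance of participants was assessed by counting returned containers and filling out a questionnaire", but no cut-off for exclusion follows.

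**Conclusion.** The concern holds in a limited form. The size and the 80% belong to a non-inferiority hypothesis, while the trial as described asks about added benefit. At the plan's own rates, superiority power at two-sided 0.05 is about 40% by Fisher's exact test at 48-50 per group and 49% if all 60 are analysed. No method examined reaches 80%, even at one-sided 0.05. Meeting the margin is not evidence of benefit, since it would happen in about 12-14% of trials with no effect at 75% cure.

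These figures assume that 0.90 and 0.75 describe the analysed cure rate; power could be lower if day-30 failures are removed from a day-90 comparison. The documents do not support the inference that a benefit claim was made, or that any criterion was chosen after the results were known. They simply do not show when a superiority criterion was fixed: the registry posting is dated, but its content is not given. The matter should be fixed; it does not make the trial unusable.

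**What to change.** Keep 120 patients.

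1. State that a claim of added benefit requires superiority, and that meeting the -0.068 margin supports only the statement that cure is not worse by more than 6.8 points.
2. Decide superiority by the test already named, Fisher's exact test at two-sided 0.05, for one stated visit and one stated denominator that counts day-30 failures as not cured. Report the cure-rate difference with a named 95% interval, to show the size of effect and to support any retained non-inferiority statement.
3. Do not make a more lenient method decisive unless it is shown to have been fixed before the data were seen. Otherwise label the superiority reading post hoc.
4. State that the 80% applies to non-inferiority only, and give the superiority power beside it: about 40% by Fisher at 48-50 per group, under the assumed rates.

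The cost is a less favourable stated power and a disclosure that the sizing was for non-inferiority. No patients are added and no treatment changes.

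### Enrolling 120 does not cover the stated 20% loss to follow-up: 48 per group would remain, against the 50 the plan requires

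*Combined protocol and SAP*

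**What the plan says.** All the figures are in the sample size paragraph under Study Protocol with SAP. The plan states: "The sample size was calculated based on the non-inferiority test". Its inputs are α = 0.05 (one- or two-sided not stated), power 0.80, Pt = 0.90, Pc = 0.75, 1:1 allocation, a margin of −0.068 and Fisher's exact test. An online calculator is cited, but no formula is given.

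The result is that "the sample size of each group was calculated as 50 patients, 100 patients in total". The allowance for loss follows: "Considering a loss to follow-up rate of 20%, a sample size of 120 patients was finally determined, with 60 patients in each group".

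Three other places bear on the point:
- The design paragraph places recruitment "between March 2019 and June 2019 with abnormal vaginal discharge symptoms were recruited".
- The randomization paragraph at the end confirms equal groups: "This study was a single-centre randomized controlled trial with two arms allocated at a ratio of 1:1".
- The outcome paragraph says: "The efficacy outcome was evaluated by the cure rate according to per-protocol (PP) analysis".

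Nothing elsewhere in the document restates or corrects the 120.

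**The concern.** A loss to follow-up rate is a share of the women enrolled. If 20% of those enrolled are lost, 80% remain, and that 80% has to be at least the number the calculation requires. With 60 enrolled per group it is not.

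The number left after losses matters here because efficacy is evaluated per protocol, so women lost to follow-up would be expected to drop out of the efficacy comparison. A reader who relies on the sentence would believe that 20% attrition still leaves the planned 50 per group. The claim at stake is that protection. The size of the shortfall does not call the design itself into question.

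**Working it through.** **Inputs, all from the sample size paragraph.** Required n = 50 per group (100 in total); loss rate d = 0.20; enrolled N = 60 per group (120 in total); Pt = 0.90; Pc = 0.75; margin 0.068; α = 0.05; power 0.80.

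**Reproducing the plan's 120.** Multiplying by (1 + d) gives the stated figures exactly: 50 × 1.2 = 60 and 100 × 1.2 = 120. That this was the step taken is an inference from the match.

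**What 120 leaves at 20% loss.** N × (1 − d):
- per group, 60 × 0.80 = 48, which is 2 short of 50
- in total, 120 × 0.80 = 96, which is 4 short of 100

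**Loss that 120 can absorb.** 1 − n/N = 1 − 50/60 = 0.167, or 10 women per group.

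**Enrolment that would cover 20%.** n/(1 − d) = 50/0.80 = 62.5, rounded up to 63 per group, 126 in total. Check: 63 × 0.80 = 50.4, which is at least 50.

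**Effect on power.** The formula and the sidedness are not stated, so these are assumptions, shown as a range. The distance from the assumed difference to the margin is 0.90 − 0.75 + 0.068 = 0.218. With S₁ = √(0.90 × 0.10 + 0.75 × 0.25) = 0.527:
- Unpooled normal: power = Φ(0.218√n / S₁ − z).
- Farrington-Manning: power = Φ((0.218√n − z·S₀) / S₁). Here S₀ = 0.553 comes from the rates restricted to the margin, 0.776 (treatment) and 0.844 (control).
- Shifted Fisher: exact power of a one-sided Fisher test of 0.90 against 0.75 − 0.068 = 0.682.

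| Method | One-sided α | Power at 48 | Power at 50 | Loss (points) |
|---|---|---|---|---|
| Farrington-Manning | 0.025 | 79.1% | 80.8% | 1.7 |
| Farrington-Manning | 0.05 | 87.3% | 88.5% | 1.2 |
| Unpooled normal | 0.025 | 81.8% | 83.3% | 1.5 |
| Unpooled normal | 0.05 | 88.9% | 90.0% | 1.1 |
| Shifted Fisher | 0.025 | 68.7% | 71.3% | 2.6 |
| Shifted Fisher | 0.05 | 79.4% | 80.7% | 1.3 |

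Three of these combinations give a required n close to the plan's 50: Farrington-Manning at 0.025 (49.05, rounded up to 50), shifted Fisher at 0.05 (49) and unpooled at 0.025 (45.83, rounded up to 46). Across those three the loss is 1.3 to 1.7 points. Power at 48 falls just below 80% under the first two and stays above it under the third.

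**The case against.** The only reading that saves 120 takes the 20% as a top-up on the 100 required. The plan does not show its formula, so this cannot be ruled out as what was done. But the sentence calls the 20% a loss to follow-up rate, which describes women lost, not women added. However 120 was reached, 20% loss from it leaves 96.

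A stronger objection is that the point has almost no practical effect. The gap is 2 women per group at the assumed loss rate, recruitment is over, and the choice of method and sidedness moves power far more than those 2 women do. In one of the six combinations above, even 50 per group misses 80% by about 9 points; in three, 48 per group is above it. The calculator's formula is not available either, so it is unknown whether 50 is the true minimum. In addition, the shifted Fisher figure is a device for approximating the calculation, not a test the plan describes.

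All of this stands as a limit on the power figures and is a reason to rate the point minor. None of it touches the comparison of 48 with the plan's own 50.

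**Conclusion.** The concern holds and is minor. At the plan's own loss rate, 120 enrolled leaves 96 evaluable (48 per group), not the 100 (50 per group) that the plan says it needs. The enrolment covers a loss of 16.7%, not 20%. This follows from the stated figures alone and needs no assumption beyond reading the loss rate as a share of those enrolled.

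The effect on power depends on assumptions: about 1.1 to 2.6 points over the six combinations, and 1.3 to 1.7 over the three whose required n lies near 50. The mismatch is a reporting error. The 2-per-group shortfall does not make the design materially underpowered.

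**What to change.** Replace the loss-to-follow-up sentence in the sample size paragraph with wording such as: *Enrolling 120 patients (60 per group) retains the required 50 per group if no more than 10 per group (16.7%) are lost to follow-up; at 20% loss (12 per group), 48 per group would remain.*

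Because efficacy is evaluated per protocol, add that this allowance covers loss to follow-up only and not other exclusions from the per-protocol set. Stating the power at 48 per group is optional; if it is given, name the formula and the sidedness used.

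The cost is one or two sentences and, if wanted, one power figure. With recruitment completed in 2019, enrolment does not change and no patients are added.

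### The plan names no model or covariate for the cure-rate comparison, so a small precision gain from the baseline Nugent score is not planned for

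*Combined protocol and SAP*

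**What the plan says.** All of this is in the combined document, under Study Protocol with SAP.

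- **Baseline data.** Eligibility is limited to "women with a Nugent's Gram stain score of 7 or higher". Participants then "complete a questionnaire on demographic characteristics, reproductive health and sexual behaviour" before they are allocated.
- **Allocation.** It is 1:1, from a random number table applied as women enrol. No strata or blocks are stated.
- **Outcome.** "The efficacy outcome was evaluated by the cure rate according to per-protocol (PP) analysis", with cure meaning a Nugent score below 7.
- **Sizing.** "The sample size was calculated based on the non-inferiority test", with cure rates of 0.90 (probiotic) and 0.75 (metronidazole), a margin of -0.068, alpha 0.05 and power 0.80. The parameter list ends "and Fisher's exact test". The result is that "the sample size of each group was calculated as 50 patients, 100 patients in total"; after a 20% allowance for loss, "a sample size of 120 patients was finally determined, with 60 patients in each group".

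Nothing states how the two cure rates are to be compared. No baseline item is named as an adjustment variable.

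**The concern.** The baseline Nugent score measures how far each woman starts from the cure threshold. A woman entering at 7 must drop one point to count as cured, and a woman entering at 10 must drop four. That makes the score a natural candidate predictor of cure, available without further data collection. With about 50 women per arm and no stratification, the arms will often differ somewhat in baseline severity. If severity predicts cure, that difference adds noise to an estimate that must be set against a 6.8-point margin. A model using the score would remove part of the noise, and the plan provides for none.

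What is at stake is the width of the confidence interval and, through it, a few points of power. There is also a smaller matter of discipline: the trial is open to researchers and patients, so a covariate chosen after the results are known would be hard to defend.

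**Working it through.** **1. The plan's own sample size.** Inputs from the sample-size paragraph: Pt = 0.90, Pc = 0.75, margin 0.068, power 0.80. The sidedness of alpha is not stated. The Farrington-Manning formula at one-sided 0.025 uses null rates of 0.776 and 0.844 (restricted maximum likelihood, difference -0.068):

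- null SD = √(0.776×0.224 + 0.844×0.156) = 0.553
- alternative SD = √(0.90×0.10 + 0.75×0.25) = 0.527
- n = (1.960×0.553 + 0.842×0.527)² / (0.15 + 0.068)² = 49.05, rounded up to 50

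This reproduces the stated 50 per group. The 60 is 50 × 1.20. A 20% loss from 60 leaves 48 evaluable per arm.

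**2. Precision without adjustment, 48 per arm.** SE = √((0.09 + 0.1875)/48) = 0.0760. The 95% half-width is 1.96 × 0.0760 = 14.9 points. Approximate non-inferiority power is Φ(0.218/0.0760 - 1.96) = 81.8%.

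**3. How often chance imbalance arises.** For a baseline factor with 50% prevalence (assumed), the exact binomial probability that the arms differ by 10 points or more is 36% at 48 per arm, 37% at 50 and 32% at 60. If cure differed by 20 points across that factor (assumed), a 10-point imbalance would move the estimate by 0.10 × 0.20 = 2 points. That is 2/7.6, about a quarter of one standard error.

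**4. What adjustment would gain.** The documents give no association between baseline score and cure, so a range has to be assumed. The simulation used 50 per arm, marginal cure of 0.90 and 0.75, and assumed shares of 30/30/25/15% for scores 7/8/9/10, with 6,000 trials per scenario. It compared the crude difference with the difference standardised from a logistic model containing treatment and numeric score. The last two columns apply the variance ratio V to step 2: half-width = 14.9 × √V and power = Φ(0.218/(0.0760√V) - 1.96).

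| Assumed odds ratio of failure per Nugent point | V (adjusted/crude) | 95% half-width, points | Power |
|---|---|---|---|
| no adjustment | 1 | 14.9 | 81.8% |
| 1.0 (not prognostic) | 1.01-1.02 | 15.0-15.1 | 81.0-81.4% |
| 1.5 | 0.98 | 14.8 | 82.5% |
| 2.0 | 0.94 | 14.4 | 84.1% |
| 2.5 | 0.90 | 14.1 | 85.6% |

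Simulation error is visible: repeat runs put V at 2.0 anywhere from 0.92 to 0.96. The mean adjusted and crude differences agreed closely in every scenario, so no bias from adjustment was detectable.

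**5. How many covariates the data can carry.** Expected failures at 48 per arm are 48×0.25 + 48×0.10 = 12 + 4.8 = 16.8, about 17. That argues for one covariate. An arm with no failures leaves the logistic fit without a finite treatment estimate. At 50 per arm and 0.90 cure this has probability 0.90⁵⁰ ≈ 0.5%, in line with failed fits in under 1% of simulated trials.

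**The case against.** Four points on the other side carry weight.

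- **The plan does not prescribe a crude comparison.** A reader might infer from the Fisher's exact entry that the plan compares crude percentages and ignores baseline. The documents do not support that. The test appears only as a sizing parameter, and no comparison method is given at all. The lack of adjustment is one part of that wider silence.
- **Unadjusted does not mean wrong.** A reader might also infer that chance imbalance would bias the result. It would not. The type I error rate and confidence interval of a randomised comparison already allow for it; in simulation, 95% intervals covered 94-95% of the time, crude and adjusted alike. Expressed against the margin, the 2-point shift in the working looks large (2/6.8 = 29%). Against the 14.9-point half-width it is small.
- **The gain is assumed.** Entry confines the score to a four-value range, and having further to fall describes the scale; it is not evidence of prognosis. At an odds ratio of 1.5 the gain is about 2%, and at 1.0 it is a small loss.
- **Adjustment is not guaranteed free of bias here.** The stated analysis is per protocol, so women are selected after randomisation and the usual assurance does not strictly apply.

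All four stand, and they limit the point to one of efficiency. They do not remove it: the score is already determined at entry, a comparison method has to be written in any case, and the potential gain exceeds the potential cost unless the score is close to non-prognostic.

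**Conclusion.** The point holds as a minor, optional gain in precision. No covariate or model is specified, although a baseline measure on the outcome's own scale exists for every woman. Under assumed odds ratios of failure per Nugent point of 1.5, 2.0 and 2.5, adjustment lowers the variance of the cure-rate difference by about 2%, 6% and 10%. That is worth about 1, 2 and 4 points of power. If the score does not predict cure, the cost is about 1-2% of variance.

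These sizes rest on the plan's cure rates and on assumed score shares and odds ratios that the documents do not supply. The planned sample size is unaffected. It would go too far to say that an unadjusted result would be invalid. It would also go too far to ask for adjustment for the questionnaire as a whole, since about 17 expected failures cannot support it.

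**What to change.** Add a short analysis paragraph to the SAP:

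- **Main analysis:** a logistic model of cure on treatment and baseline Nugent score, with the score entered as a number and no other covariate. Standardise it over the analysed women to give an adjusted difference in cure rates with a confidence interval, and compare the lower limit with -0.068. The odds ratio itself should not be used, because the margin is on the difference scale. State the confidence level and how the interval is computed.
- **Alongside:** the crude difference with its interval.
- **Fallback:** if the model does not converge, for example because one arm has no failures, the crude difference becomes the main result.

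The covariate must be fixed before outcomes are examined by arm. The document is dated February 2021 and describes recruitment from March to June 2019. If outcomes by arm have already been seen, label the adjusted estimate as added afterwards and present it as supportive.

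The cost is one model in the SAP, with no new data, visits or patients. The statistical downside is the 1-2% variance cost if the score is not prognostic.

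### Does pausing treatment during menstruation leave the probiotic course unfinished at the day-30 visit?

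*Combined protocol and SAP*

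**What the plan says.** Everything relevant is in the combined protocol and SAP, under Study Protocol with SAP, mostly in the paragraphs on treatment and outcomes.

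- **Start.** "Starting from the enrolment day, the participants in the adjunctive probiotic group received orally administered probiotic drinks", with the suppositories alongside them. The control arm receives the suppositories only.
- **Length of courses.** The probiotic is given at a stated count of "CFU per day, for 30 days", the suppositories at "0.2 g per day, for 7 days".
- **Pause.** "Therapy was initiated after the enrolment visit and suspended when menstruation began and continued immediately when it finished". No product and no arm is named.
- **Next sentence.** Advice on intercourse and douching, tied to the "first 7 days of treatment with metronidazole suppositories".
- **Visits.** "Clinical follow-up visits were scheduled at 30 and 90 days after starting treatment". Nothing moves a visit to allow for paused days.
- **Consequence of day 30.** A woman whose smear is BV positive at that visit is "excluded from the trial, but when we evaluate the overall recurrence rate of the 90-day follow-up, these participants were still included in".
- **Population.** The inclusion criteria require "premenopausal women", and long-term contraceptive users are excluded.
- **Adherence records.** Container returns, questionnaires and medication diaries are collected. No adherence threshold is given for the per-protocol set.

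**The concern.** The probiotic course and the first visit fit together with no slack: 30 daily doses from enrolment end the day before the visit. In this population most women will bleed at least once in that month. If the pause applies to the drink, something has to give: either doses are lost, or the course runs past the visit.

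The day-30 smear is the first of the two that feed the cure rate, and a positive result there removes a woman from further follow-up in the trial. Only the adjunctive arm has a 30-day product, so any shortfall falls on one side of the comparison. A reader might then wonder whether the day-30 result describes a complete course, a shortened one or one still running, and whether some women were excluded with doses still to take.

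**Working it through.** The plan states no figure on this point, so there is none to reproduce. The check is a count of days.

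**Inputs from the document.** First dose on the enrolment day (day 0); one probiotic dose a day for 30 days; one suppository a day for 7 days; visits at days 30 and 90; 60 women planned per arm.

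**Assumptions.** The document gives no cycle data. Let the cycle be *L* days with *b* bleeding days, enrolment be equally likely on any non-bleeding day, and no paused product be taken while bleeding.

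**Reading A: only the suppositories are paused.** Probiotic doses fall on days 0 to 29, so 30 of 30 are taken before the visit. The last is on day 29, one day before the smear.

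**Reading B: the drink is also paused, and missed days are not made up.** The course closes by the visit. For *L* = 28 and *b* = 5 there are 28 − 5 = 23 possible enrolment days. Each woman misses 5 doses, and one enrolment day in the 23 costs a sixth. Mean doses = 30 − (5 + 1/23) = 24.96, or 83% of 30.

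**Reading C: the drink is also paused, and 30 doses are to be completed.** The first bleed starts on day 1, 2, …, *L* − *b* with equal chance. Doses are outstanding at the visit if it starts by day 29:

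share unfinished = min(1, 29 / (*L* − *b*))

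| Cycle / bleed (days) | Share unfinished | Of 60, if all menstruate | Mean doses before visit |
|---|---|---|---|
| 28 / 5 | 100% (29 exceeds 23) | 60 | 25.0 |
| 35 / 5 | 29/30 = 97% | 58 | 25.5 |
| 40 / 5 | 29/35 = 83% | 50 | 26.1 |
| 45 / 5 | 29/40 = 73% | 44 | 26.6 |

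With 60-day cycles the share is still 29/57 = 51% (3 bleeding days) to 29/53 = 55% (7 bleeding days). So the statement that most women would be unfinished is sound, but only within reading C.

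**Where the course ends under C.** For 28/5, 17 of the 23 enrolment days give a last dose on day 34, and 6 run into a second bleed and end on day 39. Mean = (17 × 34 + 6 × 39) / 23 = 35.3. The latest case tried (21-day cycle, 7 bleeding days) ends on day 50.

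**Distance to day 90.** Reading A: 90 − 29 = 61 days. Reading C, 28/5: 51 to 56 days. Latest case: 90 − 50 = 40 days. The day-90 smear follows the course on every reading.

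**Suppositories.** A 7-dose course interrupted by one 7-day bleed ends on day 6 + 7 = 13, which is 17 days before the visit. Pausing this product creates no conflict at day 30.

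**Which reading does the text support?** It does not settle the matter. The pause names no arm, the suppository is the only treatment both arms share, and the next sentence concerns suppositories; these point towards A. On the other side, the preceding sentences speak of the trial's products collectively, which includes the drink. Nowhere does the text refer to 30 doses; a daily product for 30 days from enrolment reads at least as naturally as calendar days.

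**The case for a change.** The best case for acting runs as follows. The treatment being paused is never defined, and the collective wording just before it lets the drink in. Bleeding within the month is close to certain for ordinary cycles. Day 30 carries weight, because a positive smear there ends a woman's participation apart from the 90-day recurrence rate. The uncertainty touches one arm only. The efficacy analysis is per-protocol without a stated adherence rule, so five unused doses could be either permitted or missed. One clause would settle it.

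The silence is real, and the arithmetic stands. The consequence does not follow, for four reasons.

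- Doses are outstanding only if the drink was paused and 30 doses were also intended. The text does not favour that combination.
- The contrast at day 30 is modest. With no pause at all, the smear comes the day after the last dose, so calling the visit on-treatment under reading C changes little. In the 28/5 case the gap between readings is 30 doses against about 25.
- The plan attaches no rule to the dose count. Since there is no adherence threshold, no woman is kept or dropped because of how the pause is read. What defines the per-protocol set is a separate question, and clarifying the pause would not answer it.
- Container counts and diaries record what was taken. They do not reveal the intended rule, but they let an analyst describe exposure up to day 30.

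It is also true that the plan does not say what happens to the remaining doses of a woman excluded at day 30. That matters only under reading C, and her day-30 smear result is already fixed by then.

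**Conclusion.** No change to the plan. This is a gap in wording that the people running and reporting the trial can fill from their own records, and filling it in the plan gains nothing: no visit, endpoint, analysis, exclusion or sample size would move, and no stated rule is shown to give a wrong result.

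The size depends on the reading. It is zero if only the suppositories were paused. If the drink was paused and not made up, the course is about 5 doses short in the 28/5 case. If it was paused and made up, doses are outstanding for 73% to 100% of menstruating women across the cycles tabulated (51% at the lowest, with 60-day cycles). These are counts of doses under assumed cycle and bleeding lengths, not estimates of bias. The documents support neither a direction nor a size for any effect on the cure rates, and whichever reading applied, the trial compares the two regimens as delivered.

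Nothing here judges which product ought to be paused. A trial report can say in a clause which product was paused and what the 30 days counted, and call day 30 an on-treatment assessment if doses were still outstanding.
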